### **4.0 Study Objectives, Design and Procedures**

#### **4.1 Study Objectives**

##### **Period 1**

To compare the safety and efficacy of Upadacitinib 30 mg QD and 15 mg QD versus placebo on a background of csDMARD(s) for the treatment of signs and symptoms of RA in bDMARD-inadequate response (bDMARD-IR) or bDMARD-intolerant subjects with moderately to severely active RA.

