#### **4.2 Overall Study Design and Plan**

This is a Phase 3, multicenter study that includes two periods. Period 1 is the 24-week randomized, double-blind, parallel-group, placebo-controlled period designed to compare the safety and efficacy of Upadacitinib 30 mg QD and 15 mg QD versus placebo for the treatment of signs and symptoms of subjects with moderately to severely active RA who have an inadequate response to or intolerance to bDMARD therapy and are currently on a stable dose of csDMARDs. Period 2 is a blinded long-term extension to evaluate the

long-term safety, tolerability, and efficacy of Upadacitinib 30 mg QD and 15 mg QD in subjects with RA who have completed Period 1. Starting with Amendment 4, all subjects will receive open-label upadacitinib 15 mg QD, including those currently on upadacitinib 30 mg QD.

The study is designed to enroll approximately 450 subjects at approximately 350 study centers worldwide to meet scientific and regulatory objectives without enrolling an undue number of subjects in alignment with ethical considerations. Therefore, if the target number of subjects has been enrolled, there is a possibility that additional subjects in screening may not be enrolled.

The study duration includes a 35-day screening period; a 24-week randomized, double-blind, parallel-group, placebo controlled treatment period (Period 1); a 236-week blinded extension period (Period 2); and a 30-day follow-up (call or site visit).

Subjects who meet eligibility criteria will be randomized in a 2:2:1:1 ratio to one of four treatment groups:

- Group 1: Upadacitinib 30 mg QD, N = 150 (Day 1 to Week 12) → Upadacitinib 30 mg QD (Week 12 and thereafter)
- Group 2: Upadacitinib 15 mg QD, N = 150 (Day 1 to Week 12) → Upadacitinib 15 mg QD (Week 12 and thereafter)
- Group 3: Placebo, N = 75 (Day 1 to Week 12) → Upadacitinib 30 mg QD (Week 12 and thereafter)
- Group 4: Placebo, N = 75 (Day 1 to Week 12) → Upadacitinib 15 mg QD (Week 12 and thereafter)

Randomization is stratified by number of prior bDMARD (stratum 1: failed 1 or 2 biologics with the same mechanism of action; stratum 2: failed  $\geq 3$  biologics with the same mechanism of action and/or multiple mechanisms of action) and geographic region.

Subjects must have been receiving csDMARD therapy  $\geq 3$  months and have been on a stable dose of csDMARD(s) for  $\geq 4$  weeks prior to the first dose of study drug and must

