## **10.2.1 Analysis of Adverse Events Prior to Protocol-Defined Treatment Switching**

### **10.2.1.1 Adverse Events Overview**

The number and percentage of subjects experiencing TEAEs will be summarized by "as treated" treatment group and overall for the following AE categories.

- All TEAEs
- Treatment-emergent serious adverse events (SAEs)
- Treatment-emergent severe adverse events
- TEAEs reasonably possibly related to study drug
- TEAEs of special interest
- TEAEs leading to discontinuation of study drug
- TEAE leading to death

In the AE overview summary, any event with an unknown severity will be considered as severe and any AE with an unknown relationship will be considered as having "reasonable possibility" of being related to study drug.

Additional AEs may be considered for tabulation/summary based on recommendations from Clinical and Safety as deemed appropriate.

For TEAEs of special interest, the point estimate and 95% CI (using normal approximation) will be provided for the treatment difference in AE percentage between each Upadacitinib dose group and the combined placebo group.

As a sensitivity analysis, the AE overview summary will be repeated by randomized treatment groups (Upadacitinib 15 mg QD, Upadacitinib 30 mg QD and the combined placebo groups). In this summary, all AEs with an onset date after the first dose of study drug will be included, regardless of whether the AE occurred more than 30 days after the last dose of study drug.

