### **10.3.2.3 Assessment of Potentially Clinical Significant Laboratory Values**

The criteria for potentially clinically significant laboratory values will be determined by OMERACT criteria of Grade 3 or 4. For creatine phosphokinase and creatinine, NCI CTC criteria will be used.

The number and percentage of subjects meeting the criteria for potentially clinically significant laboratory values will be summarized by "as treated" treatment group and overall. Comparisons of the percentage of subjects experiencing a value meeting the criteria between treatment groups will be performed using Fisher's exact tests. Only p-values  $\leq 0.100$  when rounded to three digits will be presented.

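### Grade 3/4 laboratory values at Week 12 are compared by Fisher tests with p-values shown only up to 0.100 and no risk difference or confidence interval, so the table does not show how much excess risk remains possible

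*SAP*

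**What the plan says.** SAP 10.3.2.3 defines a potentially clinically significant laboratory value by grade: the criteria "will be determined by OMERACT criteria of Grade 3 or 4", with NCI CTC grading for CPK and creatinine. Two outputs follow. The first is descriptive: "The number and percentage of subjects meeting the criteria for potentially clinically significant laboratory values will be summarized by" as-treated group and overall. The second is inferential: "Comparisons of the percentage of subjects experiencing a value meeting the criteria between treatment groups will be performed using Fisher's exact tests". Only p-values at or below 0.100 "when rounded to three digits will be presented". The section does not say whether the test is one- or two-sided, or whether it is pairwise against placebo or across all groups. It plans no difference in percentages and no interval.

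For adverse events of special interest over the same 12 weeks, SAP 10.2.1.1 does plan an estimate: a point estimate and 95% confidence interval "will be provided for the treatment difference in AE percentage between each Upadacitinib dose group and the combined placebo group".

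SAP 4.1 gives the Period 1 objective as "To compare the safety and efficacy of Upadacitinib 30 mg QD and 15 mg QD versus placebo". All placebo subjects switch to upadacitinib at Week 12.

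**The concern.** Week 12 is the only point at which the trial has a concurrent placebo comparison of severe laboratory toxicity. For that comparison the only inferential output is a p-value, printed or left out according to its size. An omitted p-value can mean that the groups are much alike, or that events are too few for the test to separate them. An interval would distinguish the two by showing the largest excess still compatible with the data; the planned table does not.

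No other Week 12 laboratory analysis supplies that interval. SAP 10.3.2.1 tests mean changes, the shift tables in 10.3.2.2 carry no tests, and the liver thresholds in 10.3.2.4 are counts and percentages only. The intervals in 10.2.1.1 rest on coded adverse events. Under Protocol 6.1.1.1 a laboratory abnormality becomes an adverse event only if it leads to discontinuation, needs treatment, or the investigator judges it to be one. A graded laboratory value therefore need not appear there.

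**Working it through.** **The plan's own power figure.** The stated power of about 90% concerns efficacy only. With 10% dropout, n = 150 × 0.9 = 135 per comparison group, and z = 2.241 for two-sided α = 0.025. Power = Φ[(Δ√n − z√(2p̄(1−p̄))) / √(p0(1−p0) + p1(1−p1))].

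- ACR20, 27% vs 47%: Φ[(2.324 − 1.530)/0.668] = Φ(1.19) = 88.3%.
- LDA, 12% vs 29%: Φ[(1.975 − 1.280)/0.558] = Φ(1.25) = 89.4%.

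Both agree with about 90%. The documents give no corresponding figure for Grade 3/4 laboratory values, no expected rate for them, and no size of excess that would matter.

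**Inputs for the laboratory test.** Group sizes are from SAP 4.2. One dose: "Group 2: Upadacitinib 15 mg QD, N = 150 (Day 1 to Week 12"). Placebo: "Group 3: Placebo, N = 75 (Day 1 to Week 12"), plus Group 4 of the same size, so 75 + 75 = 150. Assumed: a two-sided pairwise test of one dose against combined placebo, and the event rates below.

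**Method.** Every pair of event counts is enumerated and weighted by the product of two binomial probabilities with n = 150. The p-value counts as shown if the two-sided Fisher p, rounded to three digits, is at most 0.100.

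| True rate, placebo vs drug | Trials with no p-value shown |
|---|---|
| 2% vs 4% | 85% |
| 1% vs 3% | 83% |
| 0% vs 2% | 82% |
| 3% vs 6% | 76% |
| 1% vs 4% | 66% |
| 5% vs 10% | 59% |
| 2% vs 6% | 57% |
| 0% vs 3% | 53% |
| 1% vs 5% | 48% |
| 1% vs 6% | 32% |
| 2% vs 8% | 29% |
| 0% vs 4% | 28% |
| 5% vs 15% | 13% |
| 1% vs 10% | 3% |

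With 135 per group, 1% vs 3% becomes 86% and 1% vs 5% becomes 54%.

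**Single results near the threshold (150 per group).**

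- 4 vs 0: p = 2 × C(150,4)/C(300,4) = 2 × 20,260,275/330,791,175 = 0.122, not shown. Difference 4/150 = 2.7 points. Miettinen-Nurminen 95% interval 0.1 to 6.7 points; Newcombe −0.3 to 6.7.
- 8 vs 2: p = 2 × (0.00084 + 0.00890 + 0.04201) = 0.103, not shown. Difference 6/150 = 4.0 points; Newcombe −0.3 to 8.9.
- 6 vs 1: p = 0.121, not shown. Difference 5/150 = 3.3 points; Newcombe −0.4 to 7.8.
- 5 vs 0: p = 0.060, shown. With no placebo events, five on drug are the fewest that produce a p-value.

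In the three results without a p-value, the upper limit is roughly 7 to 9 points, and nothing in the planned table reports it.

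**The case against.** The strongest reply is that the missing p-value is not the result. Counts and percentages are printed for every group whatever the p-value, so a split of 4 against 0 is in plain view and a reader can derive an interval. That stands. The SAP nowhere says that an omitted p-value means no difference; a reader might infer that it does, but the text does not support attributing that interpretation to the plan.

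A reader might also infer that the test misses relevant harms 48% to 83% of the time. That range belongs to one assumed scenario, 1% on placebo against 3% to 5% on drug. The documents supply no such rates and define no relevant harm. Large excesses are rarely missed. Low power also comes from the sample size, and an interval does not cure it; an interval only makes the imprecision visible.

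Nor can it be said that the filter falls on the rarest safety events. The events of special interest that do get intervals include lymphoma, active tuberculosis and MACE. Some laboratory grades may be common: Grade 3 lymphopenia in SAP Appendix A is 0.5 to 0.9 × 1000, while Protocol 5.2.2 excludes only counts below 800/µL, so a subject can enter already at Grade 3.

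The 4 vs 0 example should not be pressed too far either. The Miettinen-Nurminen interval excludes zero and the Newcombe interval does not; what they share is the upper limit. Finally, anemia, neutropenia, lymphopenia and CPK elevation are adverse event categories with planned intervals, which gives partial cover. Protocol 8.1.5.1 also describes changes in laboratory values as a descriptive analysis.

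**Conclusion.** The point holds as a gap in presentation. The placebo-controlled comparison of Grade 3/4 laboratory values has a selectively displayed p-value and no estimate of the difference or its precision, while the SAP plans both for adverse events of special interest. No observed data are hidden, and the primary efficacy result is unaffected.

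The size depends on rates the documents do not give. Across the scenarios tabulated, the chance that no p-value appears runs from about 3% to 85%, at the planned 150 per group with a two-sided pairwise Fisher test. The firm part needs no assumed rates: at 150 per group, results such as 4 vs 0 or 8 vs 2 would appear without a p-value or an interval, although the data would be compatible with an excess of about 7 or 9 points.

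**What to change.** For every laboratory criterion in SAP 10.3.2.3, present the difference in percentages with a score-type 95% interval (Miettinen-Nurminen, for example) for each upadacitinib dose against combined placebo. A score-type interval is preferable to the normal approximation used in 10.2.1.1 because zero counts are likely: for 4 vs 0 the normal approximation gives 0.0267 ± 1.96 × √(0.0267 × 0.9733/150), or 0.1 to 5.2 points, against an upper limit of 6.7 for the score interval. Show either all Fisher p-values or none. If they are kept, state that they are two-sided and pairwise, if that is what was done, and that a large p-value is not evidence of no difference.

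The cost is small: no new data, only a wider table built from counts already produced. SAP 11.1 says that Period 1 reporting was completed under version 2.0 and that version 3.0 governs only future long-term reporting. Rewording 10.3.2.3 would therefore change no analysis still to be run; the practical form is a supplementary table.

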### **10.3.2.4 Assessment of Liver Elevations**

According to FDA's Guidance for Industry "Drug-Induced Liver Injury: Premarketing clinical evaluation" (July 2009), when aminotransferase (AT) abnormalities indicating hepatocellular injury are accompanied by evidence of impaired hepatic function (bilirubin elevation  $> 2 \times \text{ULN}$ ), in the absence of evidence of biliary obstruction (i.e., significant elevation of ALP) or some other explanation of the injury (e.g., viral hepatitis, alcohol hepatitis), the combined finding (i.e., Hy's Law cases) represents a signal of a potential for the drug to cause severe DILI.

For the purpose of assessing for potential Hy's law cases, the frequencies and percentages of subjects with post baseline liver specific function test values that meet the following criteria of potential clinical interest will be summarized by "as treated" treatment group:

- $\text{ALT} \geq 3 \times \text{ULN}$

- $ALT \geq 5 \times ULN$
- $ALT \geq 10 \times ULN$
- $ALT \geq 20 \times ULN$
- $AST \geq 3 \times ULN$
- $AST \geq 5 \times ULN$
- $AST \geq 10 \times ULN$
- $AST \geq 20 \times ULN$
- $TBL \geq 2 \times ULN$
- Alkaline phosphatase  $\geq 1.5 \times ULN$
- $ALT$  and/or  $AST \geq 3 \times ULN$  and concurrent  $TBL \geq 1.5 \times ULN$
- $ALT$  and/or  $AST \geq 3 \times ULN$  and concurrent  $TBL \geq 2 \times ULN$

### **10.3.3 Analysis of Long-Term Laboratory Data**

#### **10.3.3.1 Assessment of Mean Change from Baseline and Percentage Change from Baseline in Clinical Laboratory Variables**

Analyses of mean change from baseline in continuous hematology, chemistry, and urinalysis variables which are measured longitudinally will be performed by visits and by "as treated" treatment group sequences as described in Section 10.1. For each change from baseline analysis, the following summary statistics will be presented for each treatment group sequence: sample size, baseline mean, visit mean, and the mean, standard deviation, and median of the changes from baseline.

In addition, similar analyses will be performed for percentage change from baseline in LDL-C, HDL-C and total cholesterol.

Starting with Amendment 4, all subjects will receive open-label upadacitinib 15 mg QD, including those currently on upadacitinib 30 QD. Mean change from baseline in laboratory values for subjects who switched from upadacitinib 30 mg QD to 15 mg QD will be censored at the time of dose switch, and mean change from baseline for values

post switch will be summarized separately, as described in Section 10.1. The original study baseline will be used for calculating change from baseline.

### **10.3.3.2 Assessment of Potentially Clinically Significant Laboratory Values**

Long-term laboratory data will be summarized based on the number and percentage of subjects meeting the criteria for potentially clinically significant laboratory values and by the actual treatment received at the time of the event occurrence. Starting with Amendment 4, all subjects will receive open-label upadacitinib 15 mg QD, including those currently on upadacitinib 30 mg QD. The treatment groups for summarizing potentially clinically significant laboratory values are the same as the ones for long-term AE analysis as described in Section 8.1 and Section 10.2.2. A subject can be counted under different treatment groups if he/she switched treatment and experienced potentially clinically significant laboratory values under different treatment groups.

In the evaluation of potentially clinically significant laboratory values, the baseline value will be determined by the last non-missing measurement recorded on or before the date of the first dose of study drug in the corresponding treatment group (which may be different than the first dose of study drug received in the study). For example, for a subject who started on Placebo and switched to Upadacitinib 15 mg QD, lab values under Upadacitinib 15 mg QD exposure would be evaluated against the baseline value defined as the last non-missing measurement recorded on or before the date of the first dose of Upadacitinib 15 mg QD. For subjects who switched from upadacitinib 30 mg QD to upadacitinib 15 mg QD, lab values under upadacitinib 15 mg QD exposure would still be evaluated against the baseline defined based on the first dose of Upadacitinib 30 mg QD.

A listing of all subjects with any laboratory determination meeting OMERACT criteria of Grade 3 or 4 will be provided by Grade. For creatine phosphokinase and creatinine, NCI CTC criteria will be used. For each of these subjects, the whole course of the respective parameter will be listed.

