## **8.0 Study Drug Exposure and Compliance**

### **8.1 Study Drug Exposure**

The duration of exposure to study drug will be summarized for the safety analysis set by the following groups.

1. Placebo

2. Upadacitinib 15 mg QD

This includes Upadacitinib 15 mg QD exposure from subjects starting on Upadacitinib 15 mg QD and subjects switching from placebo to Upadacitinib 15 mg QD.

3. Upadacitinib 30 mg QD

4. This includes Upadacitinib 30 mg QD exposure from subjects starting on Upadacitinib 30 mg QD and subjects switching from placebo to Upadacitinib 30 mg QD. Exposure is censored at time of dose switch from Upadacitinib 30 mg QD to Upadacitinib 15 mg QD. Upadacitinib 15 mg QD switched from Upadacitinib 30 mg QD

This includes Upadacitinib 15 mg QD exposure from subjects who switched dose from Upadacitinib 30 mg QD to Upadacitinib 15 mg QD.

Starting with Amendment 4, all subjects will receive open-label upadacitinib 15 mg QD, including those currently on upadacitinib 30 mg QD. Exposure to upadacitinib 30 mg QD (Group 3) will be censored prior to the day subject received the first dose of upadacitinib 15 mg QD, and subsequent exposure to upadacitinib 15 mg QD will be summarized under a separate group (Group 4).

The duration of exposure to study drug will be summarized for each group as specified above, with the number of subjects, mean, standard deviation, median, minimum and maximum values. In addition, the number and percentage of subjects exposed to study drug will be summarized for the following cumulative duration intervals.

- $\geq 2$  weeks
- $\geq 1$  month
- $\geq 3$  months
- $\geq 6$  months

- $\geq 9$  months
- $\geq 12$  months
- $\geq 18$  months
- $\geq 2$  years
- $\geq 2.5$  years
- $\geq 3$  years
- $\geq 4$  years

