### 10.2.2 Analysis of Long-Term Adverse Event Rates

Long-term adverse event rates will be analyzed using event rates adjusted by cumulative exposure and will be based on the actual treatment received at the time of AE occurrence. Starting with Amendment 4, all subjects will receive open-label upadacitinib 15 mg QD, including those currently on upadacitinib 30 mg QD. For subjects who previously received upadacitinib 30 mg QD, adverse events and exposure to upadacitinib 30 mg QD will be censored at the time of dose switch; subsequent adverse events and exposure

starting the day of first dose of upadacitinib 15 mg QD will be summarized under a separate group. The detailed treatment groups, including the handling of dose switch, are described in Section 8.1.

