### **10.3.3.3 Assessment of Liver Elevations**

The frequencies and percentages of subjects with post-baseline liver-specific function test values that meet the criteria of potential clinical interest (as described in Section 10.3.2.4) will be summarized by the actual treatment received at the time of the event occurrence. Starting with Amendment 4, all subjects will receive open-label upadacitinib 15 mg QD, including those currently on upadacitinib 30 QD. The treatment exposure groups for summarizing liver elevations are the same as the ones for long-term AE analysis as described in Section 8.1 and Section 10.2.2.

A subject can be counted under different treatment groups if he/she switched treatment and experienced potentially clinical significant laboratory values under different treatment groups.

A listing of potentially clinically significant liver elevations based on criteria specified above will be provided. For each of these subjects, the whole course of the respective parameter will be listed.

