#### 10.4.3 Analysis of Long-Term Vital Sign

Analyses of mean change from baseline in continuous vital signs variables which are measured longitudinally will be performed by visits and by "as treated" treatment group sequences as described in Section 10.1. For each change from baseline analysis, the following summary statistics will be presented for each treatment group: sample size, baseline mean, visit mean, and the mean, standard deviation, and median of the changes from baseline.

Long-Term Vital Sign will also be summarized based on the number and percentage of subjects meeting the criteria for potentially clinical significant vital sign values and by the actual treatment received at the time of the event occurrence. The treatment groups are the same as the ones for long-term AE analysis as described in Section 8.1 and Section 10.2.2. A subject can be counted under different treatment groups if he/she switched treatment and experienced potentially clinical significant laboratory values under different treatment groups.

In the evaluation of potentially clinically significant vital sign values, the baseline value will be determined by the last non-missing measurement recorded on or before the date of the first dose of study drug in the corresponding treatment group, similarly as described in Section 10.3.3.2.

Starting with Amendment 4, all subjects will receive open-label upadacitinib 15 mg QD, including those currently on upadacitinib 30 QD. Mean change from baseline in vital signs for subjects who switched from upadacitinib 30 mg QD to 15 mg QD will be censored at the time of dose switch, and mean change from baseline for values post switch will be summarized separately, similarly as described in Section 10.3.3.1. The treatment groups for summarizing potentially clinical significant vital sign values are the same as the ones for long-term AE analysis as described in Section 8.1 and Section 10.2.2. For the purpose of evaluating potentially clinical significant vital sign values, for subjects who switched from upadacitinib 30 mg QD to upadacitinib 15 mg QD, baseline is defined based on the first dose of upadacitinib 30 mg QD, similarly as described in Section 10.3.3.2.

A listing of all subjects with any vital sign values meeting the criteria for potentially clinically significant vital signs will be provided. For each of these subjects, the whole course of the respective parameter will be listed.

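### Long-term laboratory, liver and vital-sign abnormalities are tabulated only as percentages of subjects across exposure groups of unequal length, so follow-up time alone can reorder the active groups; add an exposure-adjusted column

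*SAP*

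**What the plan says.** Three sections of the SAP set the measure for long-term abnormal values:

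- Laboratory (10.3.3.2): "Long-term laboratory data will be summarized based on the number and percentage of subjects meeting the criteria for potentially clinically significant laboratory values".
- Liver (10.3.3.3): "The frequencies and percentages of subjects with post-baseline liver-specific function test values that meet the criteria of potential clinical interest", summarised by the treatment actually received when the event occurred.
- Vital signs (10.4.3): "Long-Term Vital Sign will also be summarized based on the number and percentage of subjects meeting the criteria".

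The groups come from the adverse-event analysis: "The treatment groups for summarizing potentially clinically significant laboratory values are the same as the ones for long-term AE analysis". SAP 8.1 defines four:

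- Placebo.
- Upadacitinib 15 mg: "This includes Upadacitinib 15 mg QD exposure from subjects starting on Upadacitinib 15 mg QD and subjects switching from placebo to Upadacitinib 15 mg QD".
- Upadacitinib 30 mg, built in the same way and censored at the switch to 15 mg.
- 15 mg received after switching from 30 mg.

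A subject may count in more than one group.

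Adverse events in these groups are treated differently (10.2.2): "Long-term adverse event rates will be analyzed using event rates adjusted by cumulative exposure", reported per 100 patient-years. SAP 10.1 does speak of a rate for abnormal laboratory and vital-sign values, among the analyses meant to account for treatment switching. The only outputs it then names for them are frequency tables and listings. None of the three sections gives a patient-year denominator or a time-to-event method.

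**The concern.** The percentage of subjects who ever cross a threshold grows with observation time and with the number of samples taken. The 8.1 groups are segments of exposure of unequal length, so their percentages mix risk with follow-up.

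The comparison at stake is between the active groups beyond Week 12: 15 mg, 30 mg, and 15 mg after 30 mg. A reader looking for a dose relationship in ALT elevations, cytopenias, CPK or blood pressure would turn to these tables. The 15 mg group has the longest follow-up, so the bias runs against the lower dose and could hide or reverse a true dose effect.

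**Working it through.** **Inputs from the documents**

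- Treatment duration: 24 + 236 = 260 weeks (Protocol synopsis), or 260 × 7/365.25 = 4.98 years. The stated total reproduces.
- Placebo: 150 subjects (75 + 75) for 12 weeks (0.23 years).
- 15 mg: 150 starters for up to 260 weeks, plus 75 placebo switchers for up to 260 − 12 = 248 weeks.
- 30 mg and 15 mg after 30 mg: split at the switch. SAP 7.0 says the switch visit may differ by subject, and no week is given.

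Planned maximum exposure is 150 × 12 weeks = 34.5 patient-years on placebo and (150 × 260 + 75 × 248) weeks = 1,103.9 patient-years on 15 mg. The 15 mg mean is 256 weeks, about 21 times placebo.

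**Assumptions**

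- One constant hazard λ, identical in all groups.
- Discontinuation hazard d of 0, 0.10 or 0.20 per year.
- Switch at Week 150 or 180, with 208 as a late case. As a plausibility check, Amendment 4 is dated 13 December 2019. That is 203 weeks after the original protocol (21 January 2016). SAP Appendix B says Period 1 reporting was completed in 2017, so the last first dose was at least 24 weeks before the end of 2017, which puts the amendment at least 102 + 24 = 126 weeks after it. Each subject's switch came at some visit after the amendment date.

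**Formula**

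Expected percentage with at least one qualifying value over t years = 100 × λ/(λ+d) × (1 − exp(−(λ+d)t)). The 15 mg figure weights starters and placebo switchers 2:1.

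For 15 mg with λ = 0.05 and d = 0: starters 1 − exp(−0.05 × 4.983) = 22.1%; switchers 1 − exp(−0.05 × 4.753) = 21.2%; pooled (2 × 22.1 + 21.2)/3 = 21.8%.

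| λ, d (per year) | Placebo | 15 mg | 30 mg (switch Week 150 / 180) | 15 mg after 30 mg (150 / 180) |
|---|---|---|---|---|
| 0.02, 0 | 0.46% | 9.3% | 5.6% / 6.7% | 4.1% / 3.0% |
| 0.05, 0 | 1.1% | 21.8% | 13.4% / 15.8% | 10.0% / 7.4% |
| 0.05, 0.10 | 1.1% | 17.4% | 11.7% / 13.5% | 9.0% / 6.8% |
| 0.05, 0.20 | 1.1% | 14.1% | 10.3% / 11.6% | 8.2% / 6.4% |
| 0.10, 0 | 2.3% | 38.8% | 25.0% / 29.2% | 19.0% / 14.2% |

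The 30 mg column is for starters. Pooling in the placebo switchers, who have 12 weeks less, gives 13.1% / 15.5% at λ = 0.05, d = 0. A Week 208 switch gives 18.1% on 30 mg and 4.9% after it. The switched group falls below 30 mg only if the switch comes after the midpoint, Week 130 (Week 136 for subjects who began on placebo).

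**Same inputs with exposure adjustment**

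First events divided by time at risk, calculated for placebo and 15 mg, return 2.0, 5.0 and 10.0 per 100 patient-years for λ = 0.02, 0.05 and 0.10 at every d tried. Under a constant hazard the artefact disappears.

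**Sampling check**

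Scheduled chemistry and haematology draws (Protocol Appendices D and F), with an assumed 0.5% chance of a qualifying value per draw:

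| Group | Draws / weeks | Draws per year | × 0.5% = per 100 patient-years |
|---|---|---|---|
| Placebo | 4 / 12 | 17.4 | 8.7 |
| 15 mg starters | 26 / 260 | 5.2 | 2.6 |
| 30 mg starters to Week 150 / 180 | 17 / 150, 20 / 180 | 5.9, 5.8 | 3.0, 2.9 |
| 15 mg after 30 mg from Week 150 / 180 | 9 / 110, 6 / 80 | 4.3, 3.9 | 2.1, 2.0 |

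For transient abnormalities, a rate per unit time would therefore show placebo more than three times as high as 15 mg with identical risk. Among the active groups the spread is about 2.0 to 3.0. Percentages, 1 − 0.995^draws, would run from 3.0% (6 draws) to 12.2% (26 draws).

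**The case against.** There is a good case that little is lost.

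- **Other long-term outputs exist.** A reader might infer that these tables are the only long-term between-group evidence on liver, blood counts, CPK and blood pressure. They are not. SAP 10.2.2.3 gives rates per 100 patient-years for the events of special interest in Table 8, including hepatic disorder, anemia, neutropenia, lymphopenia and CPK elevation. SAP 10.3.3.1 and 10.4.3 give mean changes by visit, which cumulative follow-up does not distort. What stands against this is Protocol 6.1.1.1: an abnormal value is an adverse event only if it leads to discontinuation, needs therapeutic intervention, or the investigator judges it one. Means do not show rare outliers. In the SAP these tables remain the only long-term between-group summaries of subjects meeting the measured-value criteria.
- **Placebo has an equal-time comparison.** The Week 12 analyses (10.3.2.3, 10.3.2.4, 10.4.2) provide it. This stands, and it limits the concern to the active groups, which have no equal-time counterpart beyond Week 12.
- **The tables are descriptive and exposure is visible.** No test of these percentages is planned, and 8.1 reports exposure by group. True, but the reader would have to make the adjustment unaided.
- **A rate has its own bias.** The sampling check bears this out against placebo. A reader might conclude that rates should replace percentages throughout; that would exchange one artefact for another.

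**Conclusion.** The concern holds for comparisons among the active groups. Followed as written, the SAP yields percentages that differ through follow-up alone. At an assumed 5 per 100 patient-years in every group, without discontinuation, that means about 22% on 15 mg, 13-16% on 30 mg and 7-10% on 15 mg after 30 mg. With 0.20 per year discontinuing it is still about 14%, 10-12% and 6-8%. That 15 mg exceeds 30 mg follows from the design. The position of the switched group depends on a switch after about Week 130. Hazard, discontinuation and switch week are assumptions, and a hazard that changes over time would alter the sizes.

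Two stronger readings should be resisted. A reader might infer that any difference in these tables will be nothing but follow-up; the documents show only that follow-up can produce such differences, and true drug effects may add to them. A reader might also infer that the switched group will look safest overall; on these figures placebo is lowest, at 1.1%, and the switched group is lowest only among the active groups.

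This is an inexpensive improvement to descriptive tables. It does not touch the primary analysis or Period 1 reporting, which SAP 11.1 records as complete.

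**What to change.** In SAP 10.3.3.2, 10.3.3.3 and 10.4.3:

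1. Keep the numbers and percentages of subjects.
2. Beside them, by 8.1 group, add the number of subjects with a first qualifying value in that group per 100 patient-years at risk. Time at risk runs to first event, dose switch or end of exposure. Give an exact Poisson confidence interval and total patient-years.
3. State that the rates serve mainly to compare 15 mg, 30 mg and 15 mg after 30 mg.
4. Keep the Week 12 tables as the placebo comparison, with a footnote that sampling was denser on placebo (4 draws in 12 weeks against 26 in 260), so long-term rates against placebo are not directly comparable.
5. Take the exposure definition from 8.1. The adverse-event rate sections currently point to Section 6.0, which does not contain it.

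The cost is SAP wording, one derived time-at-risk variable and slightly more programming; no new data are needed. The rate assumes a roughly constant hazard. SAP 11.1 limits version 3.0 to future long-term reporting, so the change applies to those outputs and nothing already reported has to be redone.
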